ICH	International Conference on Harmonization of Technical Requirements for Registration of Pharmaceuticals for Human Use				
IEC	Independent Ethics Committee				
IMS	Integrated Medical Safety				
i.v.	intravenous(ly)				
IRB	Institutional Review Board				
IVRS	Interactive Voice Response System				
MMF	Mycophenolate mofetil				
MPA	Mycophenolic acid (Refers to mycophenolate sodium EC or mycophenolate mofetil containing products)				
o.d.	once a day				
p.o.	oral(ly)				
REB	Research Ethics Board				
SAE	serious adverse event				

Glossary of terms

Assessment	A procedure used to generate data required by the study
Control drug	A study drug used as a comparator to reduce assessment bias, preserve blinding of investigational drug, assess internal study validity, and/or evaluate comparative effects of the investigational drug
Enrollment	Point/time of patient entry into the study; the point at which informed consent must be obtained (i.e. prior to starting any of the procedures described in the protocol)
Investigational drug	The study drug whose properties are being tested in the study; this definition is consistent with US CFR 21 Section 312.3 and is synonymous with "investigational new drug."
Medication number	A unique identifier on the label of each medication package in studies that dispense medication using an IVR system
Patient number	A number assigned to each patient who enrolls in the study. When combined with the center number, a unique identifier is created for each patient in the study.
Stage	A major subdivision of the study timeline; begins and ends with major study milestones such as enrollment,, completion of treatment, etc.
Period	A minor subdivision of the study timeline; divides phases into smaller functional segments such as screening, baseline, titration, washout, etc.
Premature patient withdrawal	Point/time when the patient exits from the study prior to the planned completion of all study drug administration and assessments; at this time all study drug administration is discontinued and no further assessments are planned
Stop study participation	Point/time at which the patient came in for a final evaluation visit or when study drug was discontinued whichever is later
Study drug	Any drug administered to the patient as part of the required study procedures; includes investigational drug and any control drugs

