Study drug discontinuation	Point/time when patient permanently stops taking study drug for any reason; may or may not also be the point/time of premature patient withdrawal
Variable	Information used in the data analysis; derived directly or indirectly from data collected using specified assessments at specified timepoints

Protocol synopsis

Title of study: Conversion from MPA to Zortress (everolimus) for GI toxicity post-renal transplantation

This study is a prospective, single-center study to evaluate the effectiveness of conversion from MMF or EC-MPS to EVR during the first year post-renal transplant in patients who experience gastrointestinal adverse effects. The primary outcome will be change in GSRS from baseline (time of conversion) to 30 days post-conversion.

In total, 25 patients will be enrolled and converted from MPA to EVR, at an initial dose of 1 mg PO BID with target everolimus troughs between 3 - 8 ng/mL. Patients who are less than one year from date of transplant with identified GI symptoms who are on immunosuppression with tacrolimus, MPA, and prednisone will be enrolled and followed for 1 year. These patients will be compared to an historical cohort of patients receiving azathioprine for safety outcomes (including rejection and graft/patient survival).

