Visit schedule and assessments

Table 7-1 lists all of the assessments and indicates with an "x" the visits when they are performed. The day of enrollment will be considered to be study Day 1. Subjects will make scheduled study visits on Day 1, at the end of Months 1, 3, 6, and 12. Subjects who discontinue their study treatment regimen should be treated according to standard of care immunosuppression and return for the assessments indicated by X in Table 6-1. If they refuse to return for these assessments or are unable to do so, every effort should be made to contact them or a knowledgeable informant by telephone to determine the subject and graft status.

Table Error! No text of specified style		A550	essment	schedule	;	
	Screening	Treatment period (post-switch)				Final study visit
	And	Month 1	Month 3	Month 6	Month 9	Month 12
	Enrollment		-	•		
Visit	1	2	3	4	5	6
Medical history	Х					
Medication history	Х	Х	Х	Х	Х	Х
Vital signs	Х	Х	Х	Х	Х	Х
Height, weight, BMI	Х	Х	Х	Х	Х	Х
Informed consent	Х					
Dispense medication and/or instruct subject regarding use	X					
Record adverse events	Х	Х	Х	Х	Х	Х
GSRS and GIQLI instruments	Х	Х	Х	Х		Х
Clinical laboratory tests	Х	Х	Х	Х	Х	Х
Tacrolimus/everolimus trough levels	Х	X	Х	Х	Х	Х
**Trough concentrations to be drawn twice weekly upon initiation and/or dosage change until therapeutic goal level is obtained						
Evidence of bacterial, viral, and fungal infection **At the following visits and at any point such infection is reported to a physician, transplant coordinator, or study coordinator	X	X	x	X	X	X

Table Error! No text of specified style in document.-1 Assessment schedule

Patient demographics/other baseline characteristics

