This includes any SAEs likely to arise from the trial indication or progression of underlying/concomitant illness (es) (e.g. progression of cancer in oncology trials), unless specified in the protocol as study specific exemptions.

Any SAE, irrespective of causality, occurring after the subject has provided informed consent and until four weeks after the subject has stopped study participation must be reported unless otherwise stated in the protocol. SAEs occurring after four weeks from ending study participation should only be reported if considered by the Investigator attributable to the exposure to the investigational drug(s) during the trial period. This includes the period in which the study protocol interferes with the standard medical treatment given to a subject, even if study treatment has not yet started (e.g. withdrawal of previous treatment during washout period, change in treatment to a fixed dose of concomitant medication).

Timelines: All serious adverse events (SAEs) from interventional clinical trials must be reported by the sites to Sponsor within 24 hours of occurrence of the SAE. The timelines for investigator initiated trials reporting to the sponsor will be done as per Third Party Study/Investigator Initiated Trial Agreement.

Follow-up reports:

SAEs will be followed until resolution or until it is judged to be permanent, and an assessment will be made at each visit (or more frequently, if necessary) of any changes in severity, the suspected relationship to the drug of interest, the interventions required to treat it, and the outcome.

The Sponsor shall support in the following-up of all SAEs so that complete information is available to maintain patient safety and also as part of any commitments by the sponsor to any Health authority OR specific Health authority follow-up requests for the product under investigation.

Pregnancies

To ensure patient safety, each pregnancy in a patient (or a patients partner) on study drug must be reported to the sponsor within 24 hours of learning of its occurrence. The pregnancy will be followed up to determine outcome, including spontaneous or voluntary termination, details of the birth, and the presence or absence of any birth defects, congenital abnormalities, or maternal and/or newborn complications.

Data review and database management

Data collection

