Data collection will occur via the RedCap system. All local staff have received training on RedCap. Multiple forms will be created, including a baseline/screening form, and visit-specific forms. Only investigators will have access and the ability to download data.

Database management and quality control

The principal investigator will take responsibility for assessing quality data entry by overseeing all data entry into the RedCap system.

Data analysis (Any or all sections may be included based on type of study)

Statistical analysis and report writing will be performed when the last subject has completed 12 months on study.

Populations for analysis

Subjects completing three months of therapy and returning for study visit #2 will be included in the primary analysis. All subjects receiving at least one dose of everolimus will be included in all outcomes related to safety.

Patient demographics/other baseline characteristics

Demographic and background information for the population will be summarized using frequency distribution (for categorical variables) and descriptive statistics of mean, median, maximum, minimum and standard deviation (for continuous variables).

Treatments (study drug, rescue medication, other concomitant therapies, compliance)

The number of patients remaining on study medication at each study visit will be recorded. Additionally, mean tacrolimus and everolimus levels will be reported at each study visit.

Analysis of the primary objective(s)

Variable

The primary variable is the resultant score derived from the GSRS, which ranges from 0 - 45, compared at enrollment and at visit 2 (end of month 3).

Statistical hypothesis, model, and method of analysis

The null hypothesis: Conversion from MPA-based immunosuppression to EVR-based immunosuppression will result in similar GSRS scores at 3 months compared to baseline.

We will analyze changes in the GSRS using a paired T-test.

Handling of missing values/censoring/discontinuations

We will not include patients in the primary analysis and subsequent analyses of efficacy if they drop out of the study. We will analyze safety endpoints from a modified ITT approach, whereby patients receiving at least one dose of everolimus are considered on therapy until the end of their study period (12 months).

Supportive analyses

A per-protocol set will be analyzed as a secondary endpoint with regards to safety endpoints, including BPAR, graft loss, and death.

Analysis of secondary objectives

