Efficacy (secondary)

We will conduct analysis of GIQLI scores at visit 2, 3, 4, and 6 compared with baseline assessment, as well as inter-visit comparisons. Additionally, we will conduct subscore analyses of the GSRS and GIQLI at each of these timepoints. The pre-specified domains of the GSRS to be analyzed will be the abdominal pain, diarrhea and reflux scores. The GIQLI subscores will be analyzed for all domains.

Safety

Safety variables to be assessed include BPAR, graft loss, death, graft function at each study visit, discontinuation from study, discontinuation from treatment, infection, SAE, notable events, laboratory tests, and vital signs. All safety analyses will be done on the safety set. Selected variables will be analyzed using all available data including data assessed.

Health-related Quality of Life

As above.

Sample size calculation

The sample size was calculated based on the myTIME study. Sample size calculation showed that a minimum sample size of 25 patients will be required to provided 80% power to detect a change from baseline of 12 points in the total GSRS score (15-105 scale) considering a 0.05 significance level and a standard deviation of 18 and allowing for a 20% dropout. A paired t test will be utilized to compare the overall GSRS score, the GSRS subscale scores, and the GIQLI from baseline.

- Assuming a 5% 1-year rate of acute rejection, we plan to evaluate 60 historical control patients to compare differences in the secondary endpoints of acute rejection, graft survival, patient survival, and infections. The historical control group will be randomly selected from a consecutive list of patients who received a renal transplant during the same study period and were maintained on MMF 500mg-1gram BID or EC-MPS 360-720mg BID, tacrolimus, and prednisone and met stated inclusion and exclusion criteria as listed below. 30 conversion patients will be enrolled and compared 1:2 with historical controls.
- Statistical analysis for the historical control comparison will utilize the Chi-squared test for events, ANOVA for renal function outcome differences and other continuous variables, and Kaplan-Meier estimates for patient and graft survival

Ethical considerations

Regulatory and ethical compliance

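### Rejection and infection to month 12 are not secured for patients who withdraw or stop attending, and the fixed 12-month Chi-squared comparison has no rule for their missing status

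*Combined protocol and SAP*

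**What the plan says.** **Who is analysed, and for how long.** Section 10.1 (Populations for analysis): "All subjects receiving at least one dose of everolimus will be included in all outcomes related to safety". Section 10.4.3 (Handling of missing values/censoring/discontinuations) adds a modified ITT rule: "patients receiving at least one dose of everolimus are considered on therapy until the end of their study period (12 months".

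**How events are compared.** Section 10.6 (Sample size calculation): "Statistical analysis for the historical control comparison will utilize the Chi-squared test for events". Kaplan-Meier is named for patient and graft survival only. Neither section says what to do with a patient whose rejection or infection status to month 12 is unknown.

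**What is collected after a patient leaves.** This depends on how the patient leaves.
- *Stops the drug only.* The Glossary says this point "may or may not also be the point/time of premature patient withdrawal". Under Visit schedule and assessments, such patients go on standard-of-care immunosuppression and come back for the scheduled assessments.
- *Stops the drug and will not or cannot return.* The same section says "every effort should be made to contact them or a knowledgeable informant by telephone to determine the subject and graft status".
- *Withdraws prematurely.* The Glossary says "at this time all study drug administration is discontinued and no further assessments are planned".

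**SAEs.** Section 8.2 makes any SAE after consent reportable "until four weeks after the subject has stopped study participation must be reported unless otherwise stated in the protocol". Later ones are reported only if the investigator attributes them to study drug. The Glossary defines the end of participation as "Point/time at which the patient came in for a final evaluation visit or when study drug was discontinued whichever is later".

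**Controls.** Under Treatment arms, the historical azathioprine patients are described as having already finished follow-up.

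**The concern.** The analysis claims 12 months at risk for every dosed patient, but planned collection does not guarantee 12 months for everyone. A Chi-squared test needs a yes or no for each patient in the denominator. With no rule for unknown status, the natural default for a patient with no recorded rejection is no.

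Take a patient who stops everolimus at month 2, moves to standard-of-care immunosuppression and refuses further visits. With no final evaluation visit, participation ends at the last dose, and routine SAE reporting closes four weeks later. A rejection at month 5 may or may not reach the database, yet the patient stays in the denominator to month 12.

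The secondary objective is whether conversion is safe. Patients who leave may be those with intolerance or interrupted immunosuppression, so their later rejections and infections matter most. Missing them lowers the everolimus rate, and the plan describes no matching gap in the controls.

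**Working it through.** **1. The plan's own figures.** The Population section gives 30 patients and 20% dropout: 30 × 0.80 = 24 completers, so 6 leavers. Section 10.6 gives 60 controls: 60/30 = 2, the stated 1:2. The only powered figure is 25 for the GSRS. A two-sided paired t test with difference 12, SD 18 and alpha 0.05 needs 20 patients (power 80.7%), and 20/0.80 = 25, which matches. No power is stated for the safety comparison. The synopsis gives 25 patients in place of 30, but 20% of either leaves the rates below unchanged.

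**2. Inputs for the size of the effect.**
- N = 30, with at most 6 unobserved after leaving. The 20% refers to staying on everolimus for the year, so 6 is an upper value.
- Risk in the 24 who stay: 5%, the 1-year rejection rate assumed in section 10.6.
- Risk p in the 6 leavers: 5%; 10% (my assumption); 30.2%, which the Background reports for MMF dose adjustment or discontinuation. The last is illustrative and does not describe everolimus leavers.
- Timing of leaving is not given. I take uniform leaving over the year, with everyone leaving at the start as the limit.
- Events before leaving are recorded. Events after leaving are unseen and counted as none.

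**3. Formulas.** With constant hazard h = −ln(1 − p):
- True rate = (24 × 0.05 + 6p)/30.
- Under uniform leaving, a leaver's chance of a recorded event is u = 1 − p/h.
- Recorded rate = (24 × 0.05 + 6u)/30.
- Limit, all leaving at the start: u = 0, so 1.2/30 = 4.0%.

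For p = 5%: h = 0.0513, u = 0.0252, recorded (1.2 + 0.151)/30 = 4.5%, true (1.2 + 0.3)/30 = 5.0%.
For p = 30.2%: h = 0.3595, u = 0.160, recorded (1.2 + 0.960)/30 = 7.2%, true (1.2 + 1.812)/30 = 10.0%.

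| Leavers' risk | True rate | Recorded, uniform | Recorded, limit | Expected events missed |
|---|---|---|---|---|
| 5% | 5.0% | 4.5% | 4.0% | 0.15 to 0.30 |
| 10% | 6.0% | 5.0% | 4.0% | 0.29 to 0.60 |
| 30.2% | 10.0% | 7.2% | 4.0% | 0.85 to 1.81 |

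The events missed are proportional to the number unobserved, so three in place of six would halve them.

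**4. Unobserved time.** Uniform leaving: 6 × 6 = 36 of 360 patient-months (10%). Limit: 6 × 12 = 72 of 360 (20%).

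**5. Sensitivity of the test.** Against 3/60 controls (5%), uncorrected Chi-squared gives p = 0.74 for 2/30, p = 0.067 for 5/30 (three further events) and p = 0.003 for 8/30 (all six leavers). These are stress cases: three unseen events is well above the 0.15 to 1.81 expected in step 3. They show only that few events are expected, so each one counts.

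**The case against.** **The gap is narrow.** Drug stoppers are asked back by default, so their adverse events, infections and laboratory tests continue. A reader might infer that collection ends for everyone who stops everolimus. The Visit schedule does not support that; the gap is confined to withdrawals and non-returners. This stands in full.

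**There is capture outside visits.** The assessment schedule asks for infections to be recorded whenever they are reported to a physician or coordinator. The biopsy section requires a biopsy for every suspected rejection, enters results in the research database, and wants local-practice biopsies recorded too. SAE reporting outlasts participation by four weeks, and longer where attributed to the drug. This stands in part: some events after leaving would probably be seen in patients still under care at this centre. None of these provisions says it continues after withdrawal, and the Glossary plans no further assessments.

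**The plan never says that unseen events are scored as none.** True. A reader might take it as a written rule, but it is an inference from a fixed set of all dosed patients, a test that cannot censor, and silence on missing status. The Safety section's remark that selected variables use all available data names no variable and adds no collection. The per-protocol safety analysis does not recover unseen events.

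**The size is easily overstated.** A reader might take 4.0% as the expected recorded rate. It is the limit in which no leaver's event is seen even before leaving. The 20% is not loss to follow-up, and pairing 30.2% with a 5% baseline mixes unlike populations: the group without GI complications in that report had 19.4%.

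**Net bias in favour of everolimus is not shown.** Retrospective controls may themselves be under-ascertained, while everolimus patients have scheduled infection checks and a 48-hour biopsy requirement. This stands. The direction of this one mechanism is clear; the net direction of the whole comparison is not.

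**Conclusion.** The plan does not secure rejection, infection and eGFR to month 12 for dosed patients who withdraw or do not return, nor non-attributed SAEs more than four weeks after participation ends. It also has no rule for analysing their status. Followed as written, the Chi-squared comparison tends to under-count everolimus rejections and infections. Death and graft loss in non-returners are largely covered by the telephone contact and the planned Kaplan-Meier estimates, so they fall outside the point.

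The size is modest at low risk: about 4.5% recorded against 5.0% true. It grows to about 7.2% against 10.0% if leavers carry the illustrative 30.2%. Both figures rest on constant hazard, uniform leaving, 5% risk in those who stay, no capture after leaving, and six unobserved patients as the upper case.

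The affected comparison is secondary and non-randomised, with no stated power, and the primary GSRS analysis is untouched. The change is worth making because it is cheap. A reader might infer that the safety conclusion is unsound without it, but given the follow-up that the plan does provide, the documents do not support that.

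**What to change.** 1. **Collection (Glossary; Visit schedule and assessments).** State that, for every dosed patient who withdraws or stops attending, and where consent allows, biopsy-proven rejection, infection, creatinine/eGFR, graft loss, death and SAEs are abstracted from the centre's transplant record to month 12. Reconcile this with the Glossary entry that plans no further assessments and with the section 8.2 SAE window.
2. **Analysis (10.4.3, with a matching line in 10.6).** For patients whose status to month 12 remains unknown, use time-to-event estimates for rejection and infection, censored at last known contact. The plan currently names Kaplan-Meier for patient and graft survival only, so this is an addition.
3. **Sensitivity analysis.** Censoring assumes that leaving is unrelated to risk, which may be untrue here. Add an analysis that counts unknown status as an event, and report the number of patients with unknown status.

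The cost is protocol wording and chart abstraction for about six patients or fewer at one centre. The everolimus event rate may look less favourable. Consent wording should allow for record review before patients start to leave.

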- 2. Presence of a preexisting significant GI condition that does not have a presumed causal relationship with MPA

- 3. Evidence of any GI disorder induced by an infection, underlying medical condition, or concomitant medication other than MPA
- 4. eGFR<35 ml/min at time of possible conversion
- 5. Proteinuria >1 gram/day at time of possible conversion
- 6. Profound bone marrow suppression at the time of possible conversion as defined as:
 - Hemoglobin <10 g/dL
 - WBC <3 K/cumm
 - Platelets <100 K/cumm
- 7. Wound healing issues at time of possible conversion (eg, wound dehiscence, wound infection, incisional hernia, lymphocele, seroma)
- 8. Elevated total cholesterol (>350 mg/dL) and/or triglycerides (>500 ng/dL) at time of possible conversion
- 9. Hypersensitivity to everolimus, sirolimus, or other rapamycin deriviatives

Investigational and reference therapy:

Investigational therapy

- Everolimus tablets 0.25 mg, 0.5 mg, and/or 0.75 mg

Study design: Patients will be selected if they experience non-infectious GI adverse effects within the first 12 months post transplant. Following selection they will have a baseline screening and enrollment with a complete medical history, medication history, vital signs and labs (including tacrolimus and everolimus levels). In addition, their adverse effects and GSRS and GIQLI will be recorded. After enrollment they will have medication history, vitals, labs (including tacrolimus), and GSRS/GIQLI and adverse events recorded at months 1, 3, 6, 9, and 12 (excepting GSRS and GIQLI at month 9).

Efficacy assessments:

- Change in GSRS from baseline to month 3
- Change in GSRS subscores from baseline to month 3
- Changes in GSRS from basline to month 6 and 12
- Change in GIQLI from baseline to month 3
- Change in GIQLI subscores from baseline to month 3
- Changes in GIQLI from baseline to month 6 and 12

Other assessments:

- BPAR rates during study (compared with historical control)
- eGFR by MDRD4 from baseline to month 12 (compared to historical control)
- Death (compared with historical control)
- Graft loss (compared with historical control)

Data analysis:

Data for primary and secondary efficacy will be compared using a paired T-test.

Background

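### Secondary efficacy: the synopsis lists 13 to 15 comparisons and section 10.5.1 implies about 39 to 45, with no testing order, adjustment or descriptive label for either list

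*Combined protocol and SAP*

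**What the plan says.** The synopsis, under Efficacy assessments, gives subscores at one time: "Change in GSRS subscores from baseline to month 3" and "Change in GIQLI subscores from baseline to month 3". Total scores are listed at month 3 and again later: "Changes in GSRS from basline to month 6 and 12" and "Changes in GIQLI from baseline to month 6 and 12". It does not say which GSRS domains are meant.

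Section 10.5.1 sets a wider programme: "GIQLI scores at visit 2, 3, 4, and 6 compared with baseline assessment, as well as inter-visit comparisons". It then adds that "we will conduct subscore analyses of the GSRS and GIQLI at each of these timepoints". On domains it says "The pre-specified domains of the GSRS to be analyzed will be the abdominal pain, diarrhea and reflux scores", and it takes all GIQLI domains. The GIQLI description gives five domains. The GSRS description under Efficacy names five GSRS domains and says their scores will be followed over time, so it does not match the three in 10.5.1.

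The synopsis (Data analysis) names the paired t-test for primary and secondary efficacy. Section 10.6 names it for total GSRS, GSRS subscales and GIQLI against baseline. The only significance level is 0.05, in the sample-size sentence for total GSRS. Nowhere is there a testing order, a key secondary endpoint, a multiplicity adjustment, or a statement that these analyses are descriptive or exploratory.

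**The concern.** Two current parts of the plan describe different sets of secondary efficacy comparisons, and the longer set is about three times the shorter. Someone analysing the data could follow either. With no rule on order or status, any domain, visit or visit pair that reaches p < 0.05 could be reported as a finding, and a reader could not tell how many comparisons it was picked from. At stake is how the secondary efficacy results can be read. The primary test and its sample size are not affected.

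**Working it through.** **The plan's own figure.** The plan states no error rate for the secondary tests, so the only figure to reproduce is the sample size in section 10.6. A paired t-test with effect 12/18 = 0.667, 80% power and 0.05 (taken as two-sided, which the plan does not state) gives n = 19.67, rounded up to 20. Allowing 20% dropout, 20/0.8 = 25. This matches.

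**Synopsis count**, taking total GSRS at month 3 as primary:
- GSRS subscores at month 3: 3 (or 5 if all domains)
- GSRS total at months 6 and 12: 2
- GIQLI total at months 3, 6 and 12: 3
- GIQLI subscores at month 3: 5
- Sum: 3 + 2 + 3 + 5 = 13, or 15 with five GSRS domains

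If the primary timepoint is 30 days, total GSRS at month 3 becomes secondary and each sum rises by one.

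**Section 10.5.1 count**, four post-baseline visits:
- GIQLI total against baseline: 4
- GIQLI total between visits: 6 if all pairs, 3 if consecutive visits only
- GSRS subscores: 3 × 4 = 12
- GIQLI subscores: 5 × 4 = 20
- Sum: 4 + 6 + 12 + 20 = 42, or 39 with consecutive pairs

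Section 10.5.1 does not itself mention total GSRS. Adding it at the three non-primary visits gives 45, or 42 with consecutive pairs. Analysing five GSRS domains instead of three adds 2 × 4 = 8, so 45 becomes 53. If inter-visit comparisons cover every scale, each of nine secondary scales has 4 + 6 = 10 comparisons and total GSRS has 9 besides the primary: 90 + 9 = 99.

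**Expected false positives** if nothing changes and 0.05 applies to each test: 45 × 0.05 = 2.25, whatever the correlation. For the synopsis list: 13 × 0.05 = 0.65.

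**Chance of at least one.** Under independence it is 1 − 0.95^45 = 0.90 for 45 tests and 1 − 0.95^13 = 0.49 for 13. Scores on related scales in the same patients are not independent, so the paired t-tests were simulated with no true change, n = 20 or 24, and between-visit correlation from 0.3 to 0.6. The documents give no correlations, so all of these are assumptions.

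| Between-scale correlation | 45 tests | 13 tests |
|---|---|---|
| 0.3 | 79–81% | 43–45% |
| 0.5 | 71–73% | 36–39% |
| 0.7 | 60–62% | 31–32% |
| 0.9 | 42–46% | 21–23% |

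The spread in each cell is mostly simulation error. The between-visit value hardly matters. If every pair of visits has correlation r, two changes from baseline have covariance 1 − r and variance 2(1 − r), so they correlate at 0.5 for any r. Sample size hardly matters either, because a t-test's false-positive rate does not depend on n.

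**The case against.** The case on the other side is substantial, and parts of it stand.

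- A reader might infer that the synopsis forbids subscore tests at other visits. It lists month 3 but excludes nothing. The two lists differ; one does not prohibit the other.
- A reader might infer that 10.5.1 as written contains 45 tests. It contains 39 to 42, and the meaning of inter-visit comparisons is not defined.
- A reader might quote a 90% chance of a false positive. That needs independent tests, which is unrealistic for domains and visits of two questionnaires in the same patients. Nor can it be said without conditions that a false positive is more likely than not, since at a correlation of 0.9 the chance is below one half.
- The 0.05 level is never assigned to secondary tests. It is carried over from the sample-size sentence as the only level available.
- The plan has one primary variable and one stated null hypothesis, its stated secondary objective is safety, and no sentence says a secondary efficacy p-value will support a claim. Strict familywise control is therefore partly a matter of preference. This supports a descriptive label as one acceptable answer, but the plan does not apply that label.
- No change on any scale is a poor description of this design. Patients enter because of current GI symptoms and there is no concurrent efficacy control, so scores may move without a drug effect. Multiplicity control does not address that.

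None of this removes the mismatch between the lists or supplies the missing rule.

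**Conclusion.** The point holds as a conflict between two lists with no rule for reading either. The synopsis gives 13 to 15 secondary comparisons. Section 10.5.1 gives 39 to 42, or 42 to 45 with total GSRS, and more on wider readings. If nothing changed and each test used 0.05, the 45-test set would produce about 2.25 false positives on average. The chance of at least one would be roughly 40% to 80%, against about 20% to 45% for the 13-test list. At any given assumed correlation the longer list carries close to twice the risk of the shorter. These ranges rest on assumed between-scale correlations from 0.9 down to 0.3, equal correlation between visits, and a two-sided 0.05 carried over from section 10.6. The count and the absence of an order, adjustment or label do not rest on those assumptions.

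**What to change.** 1. Reconcile the primary timepoint first. The opening of the synopsis gives 30 days, section 10.4.1 labels visit 2 as the end of month 3, and the assessment schedule places visit 2 at month 1. Any ordered list depends on this.
2. Make the synopsis, the GSRS description and section 10.5.1 one list. State which GSRS domains are analysed, at which visits, and what inter-visit comparisons means.
3. Choose one of two rules and write it down. Either test a short fixed sequence at 0.05 after the primary test (for example GIQLI total at the primary timepoint, then the month 12 totals), or declare all secondary efficacy descriptive.
4. Under either rule, report all subscores, other visits and inter-visit comparisons as estimates with 95% confidence intervals and no significance claim.

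This takes a few sentences and no extra patients, visits or data. The downside is fewer results that may be called significant. The change deals with chance findings only. It does not separate a drug effect from before-after change that would have occurred anyway, which would need a concurrent control.
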